### **7.3 Pregnancies**

To ensure patient safety, each pregnancy in a patient on study drug must be reported to Novartis within 24 hours of learning of its occurrence. The pregnancy should be followed up to determine outcome, including spontaneous or voluntary termination, details of the birth, and the presence or absence of any birth defects, congenital abnormalities, or maternal and/or newborn complications. Pregnant women should be encouraged to participate in the pregnancy registry to collect additional safety data on this population.

Pregnancy should be recorded on a Clinical Trial Pregnancy Form and reported by the investigator to the local Novartis Drug Safety and Epidemiology Department. Pregnancy follow-up should be recorded on the same form and should include an assessment of the possible relationship to the Novartis study drug of any pregnancy outcome. Any SAE experienced during pregnancy must be reported on the SAE Report Form.

[figure not shown]

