- The use of fingolimod in women who are or may become pregnant should only be considered if the potential benefit justifies the potential risk to fetus. Animal studies have shown reproductive toxicity including fetal loss and organ defects, notably persistent truncus arteriosus and ventricular septal defect. Furthermore, the receptor affected by fingolimod (sphingosine-1-phosphate receptor) is known to be involved in vascular formation during embryogenesis. The data available from the use of fingolimod in pregnant women are too limited to draw conclusions on safety of fingolimod in pregnancy. Since it will take approximately 2 months to eliminate the compound from the body upon stopping treatment, risk potential to the fetus may persist and contraception should be pursued during that period. The risk of teratogenic effects of fingolimod is being further addressed in a specific pregnancy registry. Fingolimod is excreted in milk of treated animals during lactation. Because of the potential for serious adverse drug reactions in nursing infants from fingolimod, women receiving fingolimod should not breast feed.
- The safety and tolerability profile did not change over time, as determined in the pooled data of the phase II and III studies and their respective open-label extension studies. In particular, the incidence of malignancies and serious infections did not increase over time. Further long-term data are however needed to better estimate the incidence of rare or time-dependent adverse events.

The current data showed no significant difference on efficacy between the fingolimod 1.25 mg/day and the 0.5 mg/day doses in phase III studies. Fingolimod 0.5 mg/day was associated with an overall more favorable risk/benefit profile than fingolimod 1.25 mg/day. Based on these data, the dose of fingolimod chosen for registration and for further clinical development is 0.5 mg/day.

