### **4.2 Exclusion criteria**

Patients fulfilling any of the following criteria are not eligible for inclusion in this study:

1. Premature permanent discontinuation from any fingolimod study due to:
  - a. An adverse event or serious adverse event or laboratory abnormality.
  - b. Conditions leading to permanent study drug discontinuation.
2. Pregnant or nursing (lactating) women where pregnancy is defined as the state of a female after conception and until the termination of gestation, confirmed by a positive

hCG laboratory test (> 5 mIU/ml). Patients who temporarily or permanently discontinued from any fingolimod study because of pregnancy or nursing (lactating) can be re-enrolled.

3. Women of child-bearing potential, defined as all women physiologically capable of becoming pregnant, UNLESS they are using highly effective contraception during the study and for 2 months after stopping treatment. ‘Highly effective contraception’ defined as contraception which results in less than 1% unwanted pregnancies when used properly according to the label.  
Women are considered post-menopausal and not of child-bearing potential if they have had 12 months of natural (spontaneous) amenorrhea with an appropriate clinical profile (e.g. age appropriate, history of vasomotor symptoms) or have had surgical bilateral oophorectomy (with or without hysterectomy) or tubal ligation at least six weeks prior to baseline. In the case of oophorectomy alone, only when the reproductive status of the woman has been confirmed by follow up hormone level assessment is she considered not of child bearing potential.
4. Chronic disease of the immune system other than MS which may require immunosuppressive treatment.
5. Severe active infection or active chronic infection.
6. Previous treatment with cladribine, cyclophosphamide or mitoxantrone.
7. Treatment with monoclonal antibodies (including Natalizumab) in the past 3 months.
8. Uncontrolled diabetes (HbA1c>9%).
9. Macular edema at Baseline.
10. Any medically unstable condition that may interfere with the patient’s ability to cooperate and comply with the study procedures, as assessed by the treating physician.
11. Any of the following cardiovascular conditions:
  - a. myocardial infarction within the past 6 months prior to enrollment or current unstable ischemic heart disease;

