## **6 Visit schedule and assessments**

[Table 6-1](#) and [6-2](#) list all assessments, and indicates with an "X" the visits when they are performed and recorded in the clinical database, with an "S" indicates when a performed

[figure not shown]
assessment is to be recorded on source documentation, and an “S1” indicates that source documentation should be present to confirm the procedure was performed as part of the previous fingolimod trial (Specific to the Baseline visit only). If an “S1” procedure was not performed in the previous trial, it has to be performed at Baseline. Assessments performed at the final visit of the previous fingolimod trial can fulfill the requirements of the Baseline only if they are completed within 14 days of enrollment in CFTY720D2399.

Patients should follow as much as possible the visit schedule with an allowed “visit window” of  $\pm 5$  days for bi-weekly visits, of  $\pm 10$  days for monthly visits, of  $\pm 14$  days for quarterly visits and of  $\pm 30$  days for bi-annual visits. If a visit was performed outside the visit window, any subsequent visits should be performed according to the original visit schedule. In the study, one month is defined as 30 calendar days.

[figure not shown]
Upon availability of the locally approved prescribing information, completion of any additional assessments required by the local label becomes the responsibility of the investigator. The assessments should be completed for all patients, unless prohibited by local regulations. Any findings qualifying as AEs/SAEs should be reported as such.

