## **7.2 Serious adverse event reporting**

To ensure patient safety, every SAE, regardless of suspected causality, occurring after the patient has provided informed consent and until 6 weeks after the patient has stopped study participation (defined as time of last dose of study drug taken or last visit whichever is later) must be reported to Novartis within 24 hours of learning of its occurrence.

Any SAEs experienced after this 6 week period should only be reported to Novartis if the investigator suspects a causal relationship to the study drug.

Recurrent episodes, complications, or progression of the initial SAE must be reported as follow-up to the original episode, regardless of when the event occurs. This report must be submitted within 24 hours of the investigator receiving the follow-up information. An SAE that is considered completely unrelated to a previously reported one should be reported separately as a new event.

Information about all SAEs is collected and recorded on the Serious Adverse Event Report Form. The investigator must assess the relationship of any SAE to study drug, complete the SAE Report Form in English, and send the completed, signed form by fax within 24 hours to the local Novartis Drug Safety and Epidemiology Department. The telephone and telecopy number of the contact persons in the local department of Clinical Safety and Epidemiology, specific to the site, are listed in the investigator folder provided to each site. The original copy of the SAE Report Form and the fax confirmation sheet must be kept with the case report form documentation at the study site.

Follow-up information is sent to the same person to whom the original SAE Report Form was sent, using a new SAE Report Form stating that this is a follow-up to the previously reported SAE and giving the date of the original report. The follow-up information should describe whether the event has resolved or continues, if and how it was treated, whether the blind was broken or not, and whether the patient continued or withdrew from study participation.

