### **10.2 Informed consent procedures**

Eligible patients may only be included in the study after providing written (witnessed, where required by law or regulation), IRB/IEC-approved informed consent, or, if incapable of doing so, after such consent has been provided by a legally acceptable representative of the patient. In cases where the patient's representative gives consent, the patient should be informed about the study to the extent possible given his/her understanding. If the patient is capable of doing so, he/she should indicate assent by personally signing and dating the written informed consent document or a separate assent form. Informed consent must be obtained before conducting any study-specific procedures (i.e. all of the procedures described in the protocol). The process of obtaining informed consent should be documented in the patient source documents.

Novartis will provide to investigators in a separate document a proposed informed consent form that complies with the ICH GCP guideline and regulatory requirements and is considered appropriate for this study. Any changes to the proposed consent form suggested by the investigator must be agreed to by Novartis before submission to the IRB/IEC, and a copy of the approved version must be provided to the Novartis monitor after IRB/IEC approval.

Women of child bearing potential should be informed that taking the study drug may involve unknown risks to the fetus if pregnancy were to occur during the study and agree that in order to participate in the study they must adhere to the contraception requirement for the duration of the study. If there is any question that the patient will not reliably comply, they should not be entered in the study.

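### Mandatory pregnancy reporting in section 7.3 has no post-dose window, although the protocol puts fetal risk at about 2 months after the last dose

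*Protocol*

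**What the plan says.** Protocol section 7.3 opens with the duty that "each pregnancy in a patient on study drug must be reported to Novartis within 24 hours of learning of its occurrence". It continues: "The pregnancy should be followed up to determine outcome, including spontaneous or voluntary termination, details of the birth". The second sentence takes its subject from the first. The next paragraph is worded without the on-drug restriction: "Pregnancy should be recorded on a Clinical Trial Pregnancy Form and reported by the investigator". Participation in the pregnancy registry is encouraged, not required.

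Two other sections state how long the drug matters after stopping. Section 1.1 says: "Since it will take approximately 2 months to eliminate the compound from the body upon stopping treatment, risk potential to the fetus may persist". Criterion 3 in section 4.2 excludes women of child-bearing potential "UNLESS they are using highly effective contraception during the study and for 2 months after stopping treatment".

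Related provisions:
- **Tests.** Table 6-1 schedules pregnancy tests at the 3- and 6-month follow-up visits and marks them for the clinical database. Table 6-2 schedules one at the 3-month follow-up visit, as source documentation only.
- **SAP.** Both the Part One and the Part Two plan (section 9.2 in each) list patients with positive pregnancy tests. Neither plans any output on pregnancy outcome.
- **Serious adverse events.** Section 7.1 counts a congenital anomaly as serious; pregnancy itself is not on the list. Section 7.2 requires reporting regardless of causality "until 6 weeks after the patient has stopped study participation", counted from the last dose or the last visit, whichever is later. Beyond that, only events with suspected causality are reportable.

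**The concern.** The protocol treats the 2 months after the last dose as a period of possible fetal exposure and sets its contraception rule accordingly. The mandatory reporting sentence does not follow that reasoning: it is tied to being on drug. A pregnancy conceived three weeks after the last dose is an exposed pregnancy on the protocol's own account, yet no explicit rule requires it to be reported within 24 hours or followed to birth.

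The primary objective is long-term safety. Section 1.1 describes fetal loss and organ defects in animals and says the human data are too limited for conclusions. Women who stop treatment, including any who stop in order to conceive, are a likely source of such pregnancies. If their outcomes are followed only at the site's discretion, the outcome data will be incomplete, and the outcomes that do arrive may be selected by the investigator's suspicion of causality.

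**Working it through.** The plan gives no figure to reproduce. The check compares time windows, in days after the last dose. The protocol (section 6) states that "one month is defined as 30 calendar days".

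**1. Period of stated risk against period of mandatory pregnancy reporting**
- Stated fetal risk and required contraception: 2 × 30 = 60 days.
- Explicit post-dose reporting window in the mandatory sentence of 7.3: 0 days.
- Not covered: 60 − 0 = about 60 days.

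**2. Would the scheduled tests find these pregnancies?**
- 3-month visit: 90 ± 14 = day 76 to 104.
- 6-month visit (Part One only): 180 ± 14 = day 166 to 194.

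Both visits fall after day 60, so a woman who returns can be found pregnant. They apply to patients who stop and do not continue fingolimod, which is the group at issue. No section links a positive result at these visits to a reporting or follow-up duty. In Part Two, Table 6-2 footnote 7 keeps the result out of the eCRF, which also sits awkwardly with the listing planned in the Part Two SAP.

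**3. Would the serious adverse event rule capture the outcome?** The window is 6 × 7 = 42 days after the later of last dose and last visit.
- Part One, 6-month visit attended: 166 + 42 = 208 to 194 + 42 = day 236.
- Part Two, 3-month visit attended: 76 + 42 = 118 to 104 + 42 = day 146.
- No visit after the last dose: day 42, which is 60 − 42 = 18 days before the risk period ends.

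Assume a term birth about 266 days after conception (my assumption; the documents give no figure). Conception between day 0 and day 60 then gives a birth at about day 266 to 326. The shortest margin is 266 − 236 = 30 days in Part One and 266 − 146 = 120 days in Part Two. The result does not depend on exactly 266: any interval from conception to birth above 236 days puts the birth outside both windows. Early losses, and some preterm births, could fall inside.

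**4. Illustrative frequency.** The risk period is 60 / 365.25 = 0.164 year.
- At 1 conception per 100 woman-years: 0.164 × 0.01 = 0.0016, or 1.6 per 1,000 women stopping.
- At 10 per 100 woman-years: 0.164 × 0.10 = 0.016, or 16 per 1,000.

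Both rates are assumptions. Criterion 3 mentions a contraceptive failure rate below 1% but gives no time unit, and the upper rate has no source in the documents. The number of women who will stop is not given either.

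**The case against.** The best case for the sponsor is the second paragraph of 7.3. It asks for pregnancies to be recorded and reported on the pregnancy form, and for follow-up on the same form, without limiting this to women on drug. Read broadly, it already covers conceptions after the last dose. This stands far enough that a reader should not infer a clear exclusion, or that sites have no duty at all. But the paragraph sets no window and reads most naturally as the procedure for the sentence before it. Two tenable readings of a safety-reporting duty, in a study planned for more than 500 centers, is itself a reason to clarify.

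Three further inferences are tempting and are not supported:
- **That these pregnancies would vanish from the data.** Part One follow-up tests enter the database, and positive results are listed. What lacks a rule is prompt reporting and outcome follow-up. Part Two is weaker, because results stay at the site.
- **That the serious adverse event window always closes 6 weeks after the last dose.** It runs from the later of last dose and last visit, so for women who attend follow-up it covers the whole 60 days and part of gestation. A birth defect also remains reportable at any time if causality is suspected, a real route given the named teratogenic risk.
- **That section 10.2 contradicts criterion 3.** It says "they must adhere to the contraception requirement for the duration of the study", which points back to the requirement in criterion 3 with its 2 months. For women who stop and do not continue fingolimod, the study also includes visits beyond 2 months. No conflict is shown.

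**Conclusion.** The point holds as a gap in the explicit reporting rule. On the mandatory wording of 7.3, 0 of about 60 days of stated fetal risk after the last dose are covered, and no other section extends pregnancy reporting or outcome follow-up to that period. The tests help detection, and the serious adverse event rule helps with early events. Neither requires a term outcome to be collected, because the all-causality window ends by day 236 (Part One) or day 146 (Part Two) even for women who attend their last follow-up visit at the latest permitted date.

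This rests on reading the second paragraph of 7.3 as procedure. On the broader reading, the section is unclear about its window instead of silent. The term-birth step also assumes more than 236 days from conception to birth. The range of 1.6 to 16 per 1,000 women stopping is an illustration under assumed conception rates, not an estimate for this trial, and the conclusion does not need it.

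**What to change.** Reconcile the reporting scope of section 7.3 with the 2-month post-treatment period in section 1.1 and criterion 3, so that a pregnancy conceived in that period falls under the same form, the same 24-hour timeline and the same follow-up to outcome as one on treatment. State in the second paragraph that it has the same scope, which removes the double reading. Section 10.2 needs no change for this purpose.

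The form, the timeline and the follow-up tests already exist, so the change is to wording in one section. The downside is a small number of additional pregnancy reports and outcome follow-ups for sites and sponsor.

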## **8 Data review and database management**

### **8.1 Site monitoring**

Before study initiation, at a site initiation visit or at an investigator's meeting, a Novartis representative will review the protocol and eCRFs with the investigators and their staff. During the study, the field monitor will visit the site regularly to check the completeness of patient records, the accuracy of entries on the eCRFs, the adherence to the protocol and to Good Clinical Practice, the progress of enrollment, and to ensure that study drug is being stored, dispensed, and accounted for according to specifications. Key study personnel must be available to assist the field monitor during these visits.

The investigator must maintain source documents for each patient in the study, consisting of case and visit notes (hospital or clinic medical records) containing demographic and medical information, laboratory data, electrocardiograms, and the results of any other tests or assessments. All information on eCRFs must be traceable to these source documents in the patient's file. The investigator must also keep the original informed consent form signed by the patient (a signed copy is given to the patient).

The investigator must give the monitor access to all relevant source documents to confirm their consistency with the eCRF entries. Novartis monitoring standards require full verification for the presence of informed consent, adherence to the inclusion/exclusion criteria, documentation of SAEs, and the recording of data that will be used for all primary and safety variables. Additional checks of the consistency of the source data with the eCRFs are performed according to the study-specific monitoring plan. No information in source documents about the identity of the patients will be disclosed.

## **8.2 Data collection**

Designated investigator staff will enter the data required by the protocol into the Electronic Case Report Forms using fully validated software that conforms to 21 CFR Part 11 requirements. Designated investigator site staff will not be given access to the EDC system until they have been trained. Automatic validation programs check for data discrepancies and, by generating appropriate error messages, allow the data to be confirmed or corrected before transfer of the data to the CRO working on behalf of Novartis. The investigator must certify that the data entered into the Electronic Case Report Forms are complete and accurate. After database lock, the investigator will receive a CD-ROM or paper copies of the patient data for archiving at the investigational site.

## **8.3 Database management and quality control**

Designated CRO personnel working on behalf of Novartis review the data entered into the eCRFs by investigational staff for completeness and accuracy and instruct the site personnel to make any required corrections or additions. Queries are sent to the investigational site using an electronic data query. Designated investigator site staff is required to respond to the query and confirm or correct the data.

Concomitant medications entered into the database will be coded using the WHO Drug Reference List, which employs the Anatomical Therapeutic Chemical classification system. Medical history/current medical conditions and adverse events will be coded using the Medical dictionary for regulatory activities (MedDRA) terminology.

Laboratory samples will be processed centrally and the results will be sent electronically to the designated CRO (Part One only).

MRI readings will be processed centrally and the results will be sent electronically to the designated CRO.

ECGs will be done locally and the outcomes will be entered into the database.

Data about all study drug dispensed to the patient and all IRT recorded information will be tracked using an Interactive Response Technology system (IRT). The system will be supplied by a vendor, who will also manage the database. The database will be sent electronically to a designated CRO.

## **9 Data analysis**

Unless otherwise mentioned, all data collected from the first dose of fingolimod in the original core/extension studies, if available, and in this long-term follow-up study will be analyzed to evaluate the long-term safety, tolerability, and effectiveness of fingolimod 0.5 mg/day in patients with MS. The baseline relative to the first dose of fingolimod (FDF baseline) will be used where change from baseline is analyzed. All the summaries will be provided by the highest assigned fingolimod dose, (i.e., fingolimod 0.5 mg/day) and any dose of fingolimod.

During Study Part Two, only adverse events, first dose monitoring, vital signs, Ophthalmological exam/OCT, and relapse are collected. The analysis including data from Study Part Two will be specified in the relevant sections.

The follow-up data after discontinuation of the study treatment in Study Part One or Study Part Two will also be summarized where appropriate.

Summary statistics for continuous variables will include N, mean, standard deviation, minimum, lower quartile, median, upper quartile and maximum.

Summary statistics for discrete variables will be presented in terms of absolute and relative frequencies. AE incidence adjusted by exposure is also used to evaluate the risk over time and presented as number of patients experiencing at least one event per 100 patient years of the at-risk population.

